## 1. Objectives

### 1.1. Purpose, specific aims, or objectives:

Aim 1. To determine feasibility and initial effectiveness of *iCanCope with Sickle Cell Pain* in youth with SCD pain.

Aim 2. To test if differences in self-efficacy, self-management behaviors, goal-setting, and perceived social support will predict changes in pain intensity and coping strategies in youth with SCD.

Aim 3. To examine possible moderators of effects of *iCanCope with Sickle Cell Pain* including engagement with treatment, demographic factors (family income, age, sex), and disease characteristics (SCD pain burden).

### 1.2. Hypotheses to be tested:

Youth who receive *iCanCope with Sickle Cell Pain* will achieve greater increases in adaptive coping and significant reductions in symptoms of pain and pain-related disability (primary outcomes) as well as significant improvements in physical and emotional functioning and disease-specific health-related quality of life (secondary outcomes) at post-treatment and 6-month follow-up compared to youth who receive the attention-control condition. Feasibility and acceptability will be demonstrated by high levels of treatment engagement and high ratings of satisfaction with the intervention.

## 2. Background

### 2.1. Relevant prior experience and gaps in current knowledge:

Limitations of Studies to Date	Proposed iCanCope with Sickle Cell Pain Study

 
• Poor user adherence.
 
• Small patient samples and included those individuals with infrequent SCD pain.
 
• Limited pain self-management content
 
	
 
✓ High accessibility using virtual delivery (app, website).
 
✓ Targeted approach to deliver pain self-management to patients with identified pain burden.
 
✓ Comprehensive self-management content based on other effective CBT pain programs that we have developed
 
✓ Adequate sample size and inclusion of individuals with clinically relevant pain as per pain burden score.
 

Advances Offered by *iCanCope with Sickle Cell Pain* Program for Youth with SCD Pain  
 Based on completed needs assessment as well as a 2014 scoping review of pain apps, the proposed *iCanCope with Sickle Cell Pain* program will be comprised of personalized goal setting to improve pain and function, CBT-based pain self-management training and rehearsal, and peer-based social support through a closed online community for youth with SCD. These components will be delivered on the *iCanCope* smartphone app and be complemented by SCD self-management education on the *iCanCope* website. The website will also include specific modules designed to empower parents and caregivers to promote disease self-management in their adolescents.

### 2.2. Relevant preliminary data:

Evaluation of Web-Based Management of Adolescent Pain ("Web-MAP")

[name] has developed an Internet delivered CBT pain intervention called Web-MAP that includes 8 weeks of online modules to teach relaxation skills, pain coping strategies, and parent behavioral and communication techniques to youth with mixed chronic pain conditions. In the initial RCT involving 48 youth (11–17 years) with a variety of pain conditions (e.g., headache, stomachache, musculoskeletal pain), significant reductions in pain and disability were found for youth receiving Web-MAP compared to a wait-list control group. Following up on this initial trial, [name] recently completed enrollment for a second large RCT of Web-MAP involving 273 youth (ages 10–17 years) with chronic pain (and their parents) recruited from pain centers around the U.S. and Canada. Adjunctive to pain clinic treatment, youth were randomized to one of two Internet treatment conditions, Web-MAP (CBT pain intervention, n=138) vs. Web-ED (education control, n=135). In our preliminary analyses, significant group-by-time interactions were found for effects of Web-MAP on children's pain-related disability (p = .03), sleep quality (p = .02), pain-related anxiety (p < .05), and parent behavior (p < .001) and distress (p = .002) at 6 months. Youth receiving the Web-MAP intervention achieved greater improvements in outcomes at 6-month follow up compared to youth receiving Internet Education.

Additional preliminary data have been collected from Web-MAP in youth with SCD to address concerns raised about youth's receptivity to learning cognitive-behavioral pain management skills. Web-MAP was piloted in 12 youth (M age = 14.2, 68% female) with SCD and their parents recruited from Connecticut Children's and Emory University (proposed sites in this application). Treatment engagement was high; youth logged into Web-MAP an average of 16.7 times (SD = 10.1, range 2–38) and parents logged in an average of 17.4 times (SD = 10.8, range = 3–43) over the 8–10 week treatment period. Youth completed an average of 6 out of 8 treatment modules and parents completed an average of 7 out of 8 treatment modules. To understand participants' experience with Web-MAP, qualitative interviews were conducted with 8 parent-child dyads. Overall, participants reported that the CBT program was a helpful tool for coping with pain: "I learned a lot about pain management and things I can do to make my load a little bit easier". However, they indicated a preference for a web program that is designed specifically for youth with SCD: "I thought Web-MAP was too simple or basic to help me. I want something more interactive that is a more real world experience". When asked what could be done to improve the web program, participants suggested developing an app: "Maybe...you could make it more accessible on your phone - like an app. That would be cool because, you know, most young adults have apps and cell phones". The proposed *iCanCope with Sickle Cell Pain* intervention will build upon the CBT pain content of Web-MAP, while significantly tailoring the program for the SCD population (largely of African descent) and to add symptom and goal tracking and peer-based social support. *iCanCope with Sickle Cell Pain* will also be delivered on an integrated smartphone and web-based platform, rather than the exclusively web-based format of Web-MAP.

#### Development and Validation of "Sickle Cell Disease Pain Burden Interview-Youth" (SCPBI-Y)

The SCPBI-Y is a brief, clinically relevant, multidimensional interview that has been validated to assess pain burden in youth aged 7–21 years with SCD. The construct of "pain burden" was defined to encompass pain, and its impact on physical function, social/community participation, and the emotional aspects of daily living. The SCPBI-Y was developed using a panel of field experts (physicians, nurses, psychologists, researchers), patients, and caregivers as well as review of existing functional assessment and pain impact tools in the literature. The validation study involved 129

youth recruited from the inpatient and outpatient clinics of 4 pediatric hospitals. The SCPBI-Y demonstrated strong internal consistency reliability ( $\alpha=0.891$ ;  $N=129$ ), cross-informant concordance (child-caregiver;  $n=40$ ,  $r=0.78$ ,  $p<0.001$ ), and test-retest reliability (outpatient setting;  $n=47$ ,  $r=0.80$ ,  $p<0.001$ ). Moderate construct validity was found with validated measures of functional ability, pain, and quality of life. These findings suggest that the SCPBI-Y scores are valid and reliable for evaluating pain burden in youth with SCD and will be used to screen youth in the proposed study.

#### Development and Validation of a Web-Based Multi-Dimensional Pain Diary for Youth with SCD

This study aimed to develop and establish the content validity of a web-based multi-dimensional pain diary for young people with SCD and conduct an end-user review to refine the prototype. Diary items were adapted from the e-Ouch®, an electronic diary measure with evidence of content validity, construct validity and responsiveness in youth with arthritis. Experts in SCD, pain, and psychometrics reviewed the items for content, language, clinical relevance, comprehensiveness, and feasibility. Two iterative cycles of expert review were conducted with 15 experts in the first cycle and 12 in the second cycle. Subsequently, two iterative cycles of in-depth cognitive interviews with patients informed the diary design and guided the modification of items to ensure they were easy to understand, quick to complete, and useful in explaining pain. These potential end-users provided positive feedback on the design and prototype of the electronic diary. The next steps for the measure will be to evaluate construct validity and responsiveness. This study provided experience in daily monitoring of pain that will inform the approach used in the proposed RCT.

#### "Teens Taking Charge: Managing Arthritis Online" Disease Self-Management Program

[name], one of the study's Co-PIs is currently completing a multi-center RCT to evaluate the effectiveness of Teens Taking Charge: Managing Arthritis Online, a 12-week multi-component web-based program consisting of disease education, self-management strategies, and social support designed for youth with arthritis and their parents. The program also includes weekly contact with telephone-based coaches (trained non-healthcare professionals). This program was developed and evaluated in English and French using a sequential phased approach, including iterative development, usability testing, and outcome evaluation. The current trial involves 324 youth (12-18 years) and one of their caregivers from 11 pediatric hospitals. 330 participants were randomized to the intervention or attention-control group. We are completing outcome data on HRQL, arthritis symptoms, treatment adherence, knowledge, and self-efficacy from both groups at baseline (T1), immediately following the intervention (T2), and at 6 (T3) and 12 (T4) months. Our group is also completing an NIH-funded trial of a Spanish version of the Teens Taking Charge program ( $n=300$ ), and have adapted the program to meet the self-management needs of youth with cancer (Funded by CIHR) and hemophilia (Canadian Hemophilia Society). All of these web-based interventions were built by AboutKidsHealth, the same team that will develop and ensure the sustainability of the *iCanCope with Sickle Cell Pain* website.

**Needs Assessment to Inform Development of *iCanCope with Sickle Cell Pain* Program**  
This study aimed to qualitatively explore the perceived pain self-management needs of young people with SCD. A descriptive qualitative design was used with a purposive sample of young people aged 12-29 years with SCD ( $n=26$ ), parents ( $n=5$ ), and healthcare professionals (HCP;  $n=34$ ). Our findings demonstrated that all young people had significant disease impact from SCD on their physical, emotional, role, and future functioning. Participants also described a lack of available resources to support disease

self-management, especially pain, and indicated that the proposed *iCanCope with Sickle Cell Pain* program could address this need (See Table 2). This is one of the first studies to explore the perceived pain self-management needs of youth with SCD with the goal of informing development of a web- and app-based self-management intervention for this population. We anticipate that this early involvement of youth, parents, and HCPs will help to ensure that the content and format of the intervention is relevant, acceptable, and meets the needs of this underserved group.

### 2.3. Scientific or scholarly background:

#### Poor Pain Self-management in Youth with Sickle Cell Disease

Sickle cell disease (SCD) is the most common genetic blood disease in North America and primarily affects people of African descent. The hallmark feature of SCD is recurrent episodes of acute severe pain due to vaso-occlusive crisis (VOC; blockage of red blood cells). SCD pain is reportedly worse than postoperative pain, as intense as terminal cancer pain, and has a negative impact on all aspects of health-related quality of life (HRQL). Youth experience increased SCD pain burden as they grow from childhood to adolescence and young adulthood. In addition to acute pain from VOC, many youth with SCD also experience daily chronic pain. The negative consequences of recurrent SCD pain include depression and anxiety, academic underachievement related to missing school, little or no opportunities for social interaction with peers, impaired physical activity, poor sleep, and high stress. The vast majority of SCD pain episodes (90%) are treated in the home setting; unfortunately, many of these episodes may not be optimally managed. Self-management has been defined as “the individual’s ability to manage the symptoms, treatment, physical, and psychological consequences and lifestyle changes inherent to living with a chronic illness”. The most successful self-management interventions are rooted in the principles of cognitive-behavioral therapy (CBT). CBT involves normalization of the patient’s experience through education, training in strategies for managing disease-related symptoms and other stressors, enhancing self-efficacy, and guidance on developing and maintaining a long-term self-management plan. Studies in pediatric and adult SCD patients demonstrate that CBT-based therapies that promote disease self-management can lead to reduced symptoms, improved HRQL, and decreased healthcare utilization. Gaining skills in monitoring and managing their SCD pain at home is particularly critical to achieve during childhood because SCD is associated with worsening pain and disability in adulthood.

#### Barriers to Providing Pain Self-Management Care for Youth with SCD and their Caregivers

Home-based pain management for SCD is typically inadequate due to a lack of appropriate training for patients and parents. Youth with SCD and their caregivers may be reluctant to seek out mental health services for pain management and when interested rarely have access to these services due to geographic restrictions (e.g., available only in tertiary centers), limited availability of trained clinicians to deliver the therapies, inaccessibility due to school and work schedules, as well as direct and indirect incurred costs if additional healthcare visits are used to provide this training. Moreover, these therapies tend to be delivered in individual or group sessions in specialty clinics by highly trained personnel, and are unsuitable for widespread distribution to community and home-based settings.

#### Rationale for Web and Mobile Technologies to Enhance Delivery of Pain Self-management Care

Web and mobile technologies can be applied to enhance the accessibility of pain self-management therapies. In addition to improving access, these technologies can empower youth to take an active role in managing their condition by providing “in the moment” access to pain coping strategies. These technologies can therefore be leveraged together to build a

tailored self-management program for youth with SCD that emphasizes empowerment, involves parents, facilitates the creation and tracking of personalized goals, and offers peer-based social support. A media-rich website delivered on a desktop/laptop computer is ideal for teaching complex CBT-related skills using animations, illustrations, and videos. Smartphones are deeply integrated into the daily life habits of most youth, and therefore offer an ideal platform to prompt practice of CBT-based coping skills as needed in the moment.

**Systematic and Meta-Analytic Reviews of Internet-Based Interventions for Pain Management**  
Outcome data for web-based disease self-management interventions have rapidly increased over the past decade. Results from systematic and meta-analytic reviews suggest consistent efficacy for symptom reduction, knowledge attainment, and improved health behaviors in individuals with painful and other chronic health conditions. In the field of chronic pain, there is emerging evidence from two recent systematic reviews in adults (e.g., 11 RCTs with a pooled effect size of |0.285|; 95% confidence interval [CI]; |0.145 to 0.424|) and one in children/adolescents (4 RCTs with a pooled effect size of |0.41|; 95% CI; |0.74 to 0.07|) that self-guided treatments delivered over the Internet reduce pain intensity. However, there is little empirical data on the availability and effectiveness of web-based pain management interventions that target the unique developmental and disease-related needs of youth (aged 12-18 years) with SCD.

**Systematic Reviews of Smartphone-Based Interventions for Pain Management**

There are a growing number of smartphone-based pain self-management applications ("apps") available for patients to download and use on their personal mobile devices. In 2014, we conducted a comprehensive scoping review of available pain self-management apps across the iPhone, Android, Windows, and BlackBerry stores. We identified 279 apps across stores with the majority (64%) designed for the Android platform. Pain self-care skill support was the most common self-management function (77.4%). Apps were also reported to provide pain education (45.9%), symptom self-monitoring (19%), social support (3.6%), and goal-setting (0.72%). No apps were comprehensive in terms of pain self-management content, with the majority of apps including only a single self-management function (58.5%). Other major limitations were noted: only 8.2% of apps included a healthcare professional in their development, patient engagement was limited, not a single app provided a theoretical rationale, and only 1 app underwent scientific evaluation.

Given that successful CBT requires strong patient engagement and consistent skills practice, it is critical that intervention content and design are relevant and appealing to end-users (i.e., youth with SCD and their families). There is a clear need to develop and test evidence-based apps to better support patients and families with accessible SCD pain self-management care.

**Existing Pain Self-Management Programs for Youth with SCD Pain**

To our knowledge, there is only one technology-based program (used in research but not publicly available) that provides pain self-management support to youth with SCD. The effectiveness of this program has been evaluated via wait-list control RCT in a sample of 46 youth (aged 8-21 years) and their caregivers. The intervention involved a single session of in-person CBT training followed by 8 weeks of home-based practice using smartphones. In comparison to control, the primary study outcome of negative thinking in response to pain was unchanged. A major study limitation was that youth did not use the smartphone app frequently. On average, youth accessed the smartphone pain coping skills on only 12% of the total days that they had the device. The range of pain frequency reported by the patient sample [mean of 15.2 pain days (SD 13.6) over 8 weeks] was relatively broad and thus some participants had relatively infrequent pain. Overall, the smartphone-assisted coping skills were used on less than 25% of total pain days. Given this low usage, the authors identified a clear need for future

studies to build strategies for increasing engagement and for properly targeting SCD patients who need pain self-management.

There are currently no standardized recommendations related to the necessary content for web and app-based pain self-management programs. In our 2014 review, we catalogued existing pain apps in terms of the presence or absence of self-management functionalities based on elements that have evidence of effectiveness. To assess app comprehensiveness, the following functions were assessed: **(a)** pain tracking, **(b)** ability to set goals related to improving pain and functioning, **(c)** training in CBT-based pain self-management strategies, **(d)** social support, and **(e)** disease-specific education.

Thus, while the one existing program for youth with SCD pain demonstrates the potential of using technology to promote pain coping in this group, it is limited by: **(a)** very low patient usage, **(b)** lack of demonstrated effectiveness for improving clinical outcomes, **(c)** lack of personalized goal-setting to improve functional outcomes, **(d)** lack of social support component, and **(e)** lack of SCD education delivered on the app. Importantly, this program also required an initial in-person CBT training session, which presents barriers in terms of cost and accessibility to many patients. (See Table 1) There is currently no single technology-based program that provides comprehensive pain coping training for youth with SCD and their caregivers.

#### **2.4. Prior approvals:**

Currently participating sites received IRB approval, this is an extension of the approved study IRB #: STUDY00000693. Before beginning the referral process at any new sites, we will ensure that approvals have been obtained and we will maintain records of their approvals including all modifications.

### **3. Study Endpoints**

#### **3.1. Primary and secondary endpoints:**

Primary endpoint is greater reductions in pain-related disability. Secondary endpoint is the reduction of pain and anxiety/depressive symptoms.

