**5.3. Data sources that will be used to collect data about subjects:**

Table 5. Study Measures					
Measure	Description of Measure P=parent report, T=teen report	Time to Complete	T1	T2	T3
	Screening and background measures				
Sickle Cell Pain Burden Interview (SCPBI)	The SCPBI will be used to screen for SCD pain burden.  (P, T)	2-3 minutes	X	X	X
Background questionnaire	This questionnaire will assess sociodemographic variables (including family income), pain characteristics such as intensity, location, and temporal features (T) and access / use / comfort with smartphones and internet technology. (P, T)	5 minutes	X		
Treatment expectancies questionnaire	7-item questionnaire to rate treatment expectancy. (P, T)	3 minutes	X		

Adolescent Sleep Wake Scale	2 items from the questionnaire will be used to screen for the optional website intervention module on insomnia.  (T)	1 minute	X		
	Primary outcome measures				
Daily pain diary (7 day)	Pain intensity (NRS-11), location, and 9-item CALI.  Completed daily for 7 days (T)	3 minutes	X	X	X
Coping Strategies Questionnaire for Sickle Cell Disease (CSQ)	The CSQ  will assess use of different strategies to cope with pain (three primary scales: coping attempts, negative thinking, passive adherence).	15 minutes	X	X	X
	Secondary outcome measures				
PROMIS-25 v1.1 Pediatric Profile	The PROMIS Pediatric Profile will be used to assess physical and emotional functioning. This is a collection of short forms containing 4 items from PROMIS domains (Depressive Symptoms, Anxiety, Mobility, Pain Interference, Fatigue, and Peer Relationships).  (T)	10 minutes	X	X	X

	items comprise each subscale.  (P)				
Treatment Evaluation Inventory (TEI)	The TEI will be used to assess acceptability (P, T)	3 minutes		X	
Patient's Global Impression of Change Scale	Change in global health / quality of life.  (T)	2 minutes		X	X
Bath Adolescent Pain Questionnaire – for parents (BAPQ-P)	The BAPQ is a measure to assess social functioning, physical functioning, depression, general anxiety, pain specific anxiety, family functioning and development. (P)	15 minutes	X	X	X
Symptom Checklist - 90	The Symptom Checklist -90 assesses a range of psychological symptoms, including obsessive compulsive, depression, anxiety, etc. (P)	12-15 minutes	X	X	X

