**10.4. Power analysis:**

Based on prior and current study experience, and the pool of available study candidates, we plan to enroll a total of 160 subjects into the pilot RCT. With attrition conservatively estimated at 20% we expect a final sample size of 128. This proposed sample size is based on the following power calculation using preliminary data from investigator experience with prior pain trials and published trials in SCD:

Calculations are based on expected differences in youth pain-related disability and pain intensity. Group sample sizes of 52 and 52 achieve 84% power to detect a difference of 1.0 in pain-related disability between the two treatment conditions, with three assessments, AR(1) covariance structure, SD=4, ICC=0.2, and alpha=0.05. If the difference is 1.5 between treatment arms, then 52 per group achieves 99% power with the same assumptions. For pain intensity, group sample sizes of 49 and 49 achieve 80% power to detect a difference of 0.75 in pain intensity (average over three time points) in a design with 3 repeated measurements having a AR(1) covariance structure, SD=2, ICC=0.2 and 0.05 alpha.

**11. Withdrawal of Subjects****11.1. Anticipated circumstances under which subjects will be withdrawn from the research without their consent:**

The PI may decide to withdraw participants from the study if a family is not able to comply with study procedures or do not understand study instructions.

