### **Analytic plan for Aim 1**

Feasibility will be determined by calculating rates of accrual, drop out, compliance, and missing data with 95% CI's. Criteria for feasibility success will be based on previous studies by our group: accrual rates >70%, attrition rates <20%, minimal technical difficulties (i.e., reported by <10%), high acceptability and satisfaction (item mean score of 4 on AES), adherence rates >80%, and minimal missed responses. In Aim 1, we will also determine preliminary efficacy of the intervention. To account for clustering due to repeated assessments within individuals, generalized estimating equations (GEE) will be used. Interaction terms will be used to compare the mean change from pre-treatment to post-treatment for the *iCanCope* group with the corresponding mean change for the *Attention Control Education* group. Single degree of freedom contrasts will test if there is a statistically significant change in pain and coping from pre-treatment to immediate post-treatment for the two groups separately; additional contrasts will be computed to test if there is a statistically significant mean change from baseline to the 6-month follow-up for each group. Secondary treatment outcomes (physical and emotional function, HRQL) will also be examined using GEE to test significant mean changes over time and between groups by using interaction terms and contrasts. Treatment fidelity will be assessed by examining differential attrition (completers vs. non-completers) between and within groups using chi-squared tests and logistic regression models.

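### The primary outcome differs between sections 1.2, 3.1 and Table 5, and section 14.1 neither names disability nor writes a between-group contrast for the primary outcomes at 6 months

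*Combined protocol and SAP*

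**What the plan says.** All of this is in the combined protocol and SAP.

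- **3.1, endpoints:** "Primary endpoint is greater reductions in pain-related disability. Secondary endpoint is the reduction of pain and anxiety/depressive symptoms". Coping is not mentioned and no measure is named.
- **1.2, hypotheses:** "greater increases in adaptive coping and significant reductions in symptoms of pain and pain-related disability (primary outcomes"), with the comparison made "at post-treatment and 6-month follow-up compared to youth who receive the attention-control condition". Physical and emotional functioning and health-related quality of life are the secondary outcomes.
- **5.3, Table 5:** two instruments sit under the primary heading. One is the 7-day diary ("Pain intensity (NRS-11), location, and 9-item CALI"), where the CALI is the activity-limitation measure. The other is the CSQ ("three primary scales: coping attempts, negative thinking, passive adherence").
- **10.4, power:** "Calculations are based on expected differences in youth pain-related disability and pain intensity". Coping has no power statement.
- **14.1, Aim 1:** "Interaction terms will be used to compare the mean change from pre-treatment to post-treatment" between the two arms, with no outcome named. The next contrasts concern "change in pain and coping from pre-treatment to immediate post-treatment for the two groups separately". Further contrasts, from baseline to 6 months, are also written for each group. Secondary outcomes are then given a GEE analysis with tests between groups.
- **14.1, Aim 2:** the outcomes are pain intensity and coping strategies. Disability appears nowhere in 14.1.

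**The concern.** Pain is primary in 1.2 and Table 5 but secondary in 3.1. Coping is primary in 1.2 and Table 5 and missing from 3.1. The only primary outcome in 3.1 is never named in the analysis section. These are all current sections, and none is said to take precedence.

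Two consequences follow. First, if pain improves significantly and disability does not, the trial meets its primary outcome on one reading and fails on another, and the choice could be made after the results are known. Second, 1.2 claims superiority over control at 6 months, but 14.1 writes the 6-month contrasts for the primary outcomes separately by arm. A significant change in one arm and a non-significant change in the other is not a test of the difference between them.

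**Working it through.** **Sections side by side**

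| Place | Disability | Pain | Coping |
|---|---|---|---|
| 1.2 | primary | primary | primary |
| 3.1 | only primary | secondary | absent |
| Table 5 | primary (diary CALI) | primary (diary NRS-11) | primary (CSQ) |
| 10.4 | sized | sized | not sized |
| 14.1, Aim 1 contrasts that name an outcome | absent | within group | within group |
| 14.1, Aim 2 outcomes | absent | yes | yes |

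The secondary list in 14.1 follows 1.2 rather than 3.1, because pain is not in it. Physical function in that list cannot stand in for disability, because 1.2 lists the two separately and at different levels.

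**How often the readings would disagree: inputs**

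- From 10.4: disability difference 1.0, SD 4; pain difference 0.75, SD 2; AR(1) with correlation 0.2; three assessments; alpha 0.05; final sample 128.
- Assumed: two-sided tests, 1:1 allocation (128/2 = 64 per arm), and a correlation r between the two outcomes' test statistics of 0 to 0.8.

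**Step 1: reproduce 10.4.** The SD of a three-assessment average is SD × sqrt((3 + 4×0.2 + 2×0.04)/9) = 0.657 × SD.

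- Pain, 49 per arm: noncentrality 0.75/(2 × 0.657 × sqrt(2/49)) = 2.83, power 80%. This matches 10.4.
- Disability, 52 per arm: 1.0/(4 × 0.657 × sqrt(2/52)) = 1.94, power about 49%. 10.4 states 84%.
- An SD of about 2.63 would give roughly the stated 84%. That value is back-calculated and appears nowhere in the documents. It is also 4 × 0.657, so applying the averaging factor twice would give the same result.

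The disability inputs and the stated power therefore disagree, so the steps below use both SDs.

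**Step 2: power at 64 per arm on the three-assessment average,** with sqrt(2/64) = 0.1768.

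- Pain: 0.75/(2 × 0.657 × 0.1768) = 3.23, power 89%.
- Disability, SD 4: 1.0/(4 × 0.657 × 0.1768) = 2.15, power 57%.
- Disability, SD 2.63: 1.0/(2.63 × 0.657 × 0.1768) = 3.28, power 90%.

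**Step 3: the same for baseline-to-T2 change,** the comparison that 14.1 writes out. The change SD is SD × sqrt(2 × (1 − 0.2)) = 1.265 × SD. Power is 38% for pain, and 20% (SD 4) or 39% (SD 2.63) for disability.

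**Step 4: pain significant and disability not** = pain power minus the probability that both are significant, from bivariate normal test statistics. On the average with SD 4, both are significant with probability 0.510 (r=0) to 0.566 (r=0.8), so 0.894 − 0.510 = 0.384 and 0.894 − 0.566 = 0.328.

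| Contrast | Disability SD | Disability power | Pain significant, disability not (r=0.8 to r=0) |
|---|---|---|---|
| Three-assessment average | 4 | 57% | 33-38% |
| Three-assessment average | 2.63 | 90% | 4-9% |
| Baseline-to-T2 change | 4 | 20% | 21-31% |
| Baseline-to-T2 change | 2.63 | 39% | 9-23% |

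**The case against.** The strongest reply is that 14.1 can be read sensibly. Its interaction sentence introduces preliminary efficacy, and the later sentence says secondary outcomes will *also* be examined by GEE with interaction terms. By context, then, the pre- to post-treatment interaction is the main test for the primary outcomes. The 6-month contrasts are called *additional*, and 5.1 presents T3 as a check on maintenance, so post-treatment is the implied main time point.

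This stands in part. A reader might infer that the primary outcomes have no between-group test at all, or that the plan gives no hint of a primary time point. The documents support neither. What remains is that the interaction does not say which outcomes it covers, while 1.2 and 3.1 disagree on that. The time point is implied rather than stated, although 1.2 names both. A fitted GEE could supply a 6-month between-group contrast, but 14.1 does not write one for the primary outcomes.

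A reader might also infer that three or more primary measures inflate the false-positive rate. That would need a rule that any one success counts, and the plan states no such rule. Section 1.2 joins its outcomes with *and*, so it can be read as requiring all of them, which lowers power but does not inflate error. Nor does Table 5's wording on the CSQ make each of its scales a separate endpoint.

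Finally, this is a pilot with explicit feasibility criteria. That lessens the consequence. It does not reconcile the sections, since 1.2 states superiority hypotheses, 10.4 gives power for two of the outcomes and 14.1 tests for significance.

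**Conclusion.** The concern holds and must be fixed. Following different sections leads to different primary conclusions, and the 6-month contrasts written for the primary outcomes do not test the hypothesis in 1.2. Both points rest on the text alone.

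The size is uncertain. On 10.4's three-assessment average, pain would be significant and disability not in about 33-38% of trials at SD 4, but in only about 4-9% at SD 2.63. A reader might take the one-in-three figure as established. It is not, because it depends on a disability SD that does not reproduce 10.4's own power. The range assumes two-sided tests, 64 per arm, 10.4's differences as the true effects, and outcome correlations from 0 to 0.8.

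**What to change.** Before outcome data are analysed by group, amend 1.2, 3.1, Table 5, 10.4 and 14.1 so that they agree:

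1. Name the same primary outcome or outcomes, the measure, the time point (or time average) and the between-group contrast in all five places. The choice is the sponsor's. One option is the disability endpoint of 3.1, measured by the diary CALI of Table 5, with pain and coping secondary. Section 3.1 names no measure itself, so the measure has to be added.
2. If several primaries are kept, state whether all must be shown (no alpha adjustment) or any one suffices (with an adjustment such as Holm). Say which CSQ scale or scales represent adaptive coping.
3. Name the outcome or outcomes in 14.1's group-by-time interaction, and add a between-group contrast at 6 months for the primary outcome or outcomes.
4. Restate 10.4's power for the chosen outcome and contrast, with the disability SD settled.

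The cost is wording and one added contrast, with no new data collection. The downside is real: some outcomes lose primary status or face a stricter test, and the stated power may become less favourable. As this is a pilot, efficacy may be better presented as between-group estimates with 95% confidence intervals.
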